### 4.3.2 Study Visits and Procedures

[figure not shown]

Figure 2. Timeline of participation. Those in the 1st row are regarded as within normal clinical

practice. Those in the 2nd row are regarded as outside of normal clinical practice.

### **4.3.3 Final Study Visit:**

The final physical study visit for individuals without complications/recurrence will be at 4-6 weeks post operatively. As none of the visits are outside of normal practice, no remuneration is required.

### **4.3.4 Post Study Follow up and Procedures**

The phone interview at 3-months and 1-year post-operatively would not be regarded as a visit. However, if the patients highlight symptoms suggestive of a complication or recurrence of symptoms, they would be offered to return for an evaluation by a colorectal specialist. It would then be dependent on the patient if they would like to take up this offer.

## **4.4 Discontinuation/Withdrawal**

### **4.4.1 Discontinuation Criteria**

Discontinuation criteria of the trial would either be due to:

- a. Safety issues of LAH techniques
- b. Significant number and severity of the complications
- c. Statistically overwhelming evidence that 1 method is superior over the other

### **4.4.2 Discontinuation Visit and Procedures**

Upon voluntary withdrawal, participants would resume regular follow up as per clinical requirement. These patients would not receive a phone interview at 3-months and a year after the procedure. These patients would also be given an open date in the clinic to allow them a year in duration to return to the clinic for evaluation if there are recurrence of symptoms or development of a previously unrecognised complication from either of the procedures.

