### **2.3 Secondary Objectives**

- Operative duration
- Incidence of post-operative bleeding
- Incidence of readmission to haemorrhoidectomy/haemorrhoidoplasty related symptoms/condition (pain/pelvic symptoms/bleeding)
- Procedure-related complications (thrombosis, fistulation, incontinence, stenosis)
- Incidence and timing of recurrence of haemorrhoid-related symptoms
- Haemorrhoid-specific QoL questionnaire (Haemorrhoid Severity Score)

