### **3.5 Subject Replacement**

Subjects who drop out are accounted for in the sample size calculation and will not be replaced.

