## 4.3 Study Visits and Procedures

### 4.3.1 Screening Visits and Procedures

Patients will be seen in the clinic or in the wards for symptomatic haemorrhoids. All these patients would be approached and be introduced to this study but not recruited yet.

Figure 2 illustrates the visits commitment throughout the study process. After the completion of surgery, patients typically would already have a follow up appointment at 4-6 weeks after the procedure. The clinician will assess the patients progress and examining them for any complications. If their recovery is smooth, most of these patients would be discharged from follow up. During the same setting, the research administrators would collect back the peri-operative package from the patient.

Research administrators would then conduct a phone interview with the patients at 3-month and 1-year after surgery to perform the QoL survey and also looking out for late-onset complications and recurrence of symptoms. If present, they will be offered to have an appointment booked with their primary surgeon. Patients would be informed of the allocation at the clinic review at 4-6 weeks. As none of the visits are outside of normal practice, no remuneration is required.

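### Section 4.4.2 cancels the 3-month and 1-year interviews for every voluntary withdrawal without asking whether the patient would still accept them, which can bias secondary outcomes

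*Protocol*

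**What the plan says.** Section 4.4.2 of the Protocol deals with voluntary withdrawal in three steps.

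- Clinical care goes on: "Upon voluntary withdrawal, participants would resume regular follow up as per clinical requirement".
- Trial contact stops: "These patients would not receive a phone interview at 3-months and a year after the procedure".
- The patient may come back on their own initiative if symptoms recur or a new complication appears: "These patients would also be given an open date in the clinic to allow them a year in duration to return to the clinic".

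The section does not distinguish a patient who refuses all further contact from one who would still answer a call or allow use of their records. It does not mention data already recorded.

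The cancelled interviews carry the quality-of-life survey and the enquiry about late complications and recurrence (sections 4.3.1 and 6.5). One secondary objective that depends on them is "Incidence and timing of recurrence of haemorrhoid-related symptoms" (section 2.3). The hypothesis in section 2.1 also names quality of life at 3 months.

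The pain scores follow another route. Section 4.3.1 says "patients typically would already have a follow up appointment at 4-6 weeks after the procedure", and at that visit "the research administrators would collect back the peri-operative package from the patient".

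On dropout in general, section 3.5 says "Subjects who drop out are accounted for in the sample size calculation and will not be replaced". Section 9.1 sets the allowance at 10% loss to follow-up.

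**The concern.** Allocation is opened only once the patient has been examined under anaesthesia (section 4.1), and the treatment is one operation. A patient who withdraws after allocation has therefore, in practice, already been treated. No study treatment is left to stop, so cancelling the calls removes only information.

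Withdrawal is unlikely to be unrelated to outcome. A painful recovery, a complication or a disappointing result could each prompt it. So could learning the allocation at the 4-6-week review, which comes before both calls. Any of these could act differently in the two arms. If so, the patients still interviewed at 3 months and 1 year are no longer comparable groups.

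At stake are recurrence, late complications and later quality of life. All are secondary, but section 1.2.1 justifies the trial partly by the lack of well-designed randomised evidence on longer-term outcomes of the laser technique.

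**Working it through.** **1. Is there another scheduled source for the later outcomes?**

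- Section 4.3.1: most patients who recover smoothly are discharged at 4-6 weeks.
- Section 4.3.3: for patients without complication or recurrence, that is the last physical visit.
- Section 4.4.2: the open date depends on the patient choosing to return, and is not said to supply trial data.

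So nothing is scheduled at 3 months or 1 year except the calls. Even if open-date visits were counted, withdrawn patients would be followed passively and the others actively, and the two are not comparable.

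**2. What does the 10% allowance cover?**

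Inputs from section 9.1: 50% against 25% with VAS above 7.5, 80% power, 5% alpha (two-sided assumed, as sidedness is not stated), 10% loss.

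n per arm = [1.960 × √(2 × 0.375 × 0.625) + 0.842 × √(0.50 × 0.50 + 0.25 × 0.75)]² / 0.25² = 57.7, rounded up to 58.

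Inflation: 58 × 1.10 = 63.8, rounded up to 64, which is the plan's figure. (58 / 0.90 = 64.4, rounded up to 65.)

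A 10% loss is 0.10 × 64 = 6.4 per arm and leaves 57.6. By the same approximation, power is 79.5% at 57 and 80.2% at 58 per arm. The allowance does what it was built for: it preserves the number analysed for the primary outcome. It says nothing about which patients are missing.

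**3. How large could the selection effect be?**

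The protocol gives neither a withdrawal rate nor a recurrence rate, so all inputs in this step are assumptions. Let a share w of each arm withdraw and not be interviewed. Let recurrence be 10% in all COH patients and in LAH patients who stay, and r among LAH patients who withdraw.

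- True LAH rate = (1 − w) × 0.10 + w × r
- Observed LAH rate = 0.10
- Understatement of the difference = w × (r − 0.10)

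| r | True LAH rate, w = 10% | Understated, w = 10% | Understated, w = 5% |
|---|---|---|---|
| 10% | 10% | 0 points | 0 points |
| 20% | 11% | 1 point | 0.5 points |
| 30% | 12% | 2 points | 1 point |
| 50% | 14% | 4 points | 2 points |

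If the excess recurrence were among COH withdrawers instead, the error would have the same size and the opposite sign. If withdrawal is unrelated to outcome in both arms, as in the first row, there is no bias.

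**4. Does the rule reach the primary outcome?**

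Pain is scored over the first 10 days (section 2.2), before either call. The package is handed in at a usual-care visit that withdrawn patients may still attend, and section 4.4.2 does not say it goes uncollected. Section 4.3.1 names no other collection point. Pain data are therefore exposed only if a patient withdraws early and also misses that visit.

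**The case against.** A reader might infer that section 4.4.2 ends all follow-up and throws away recorded pain scores. The text does not support this. Regular clinical follow-up continues, an open date runs for a year, and the pain package is due at the routine 4-6-week visit. Withdrawal prompted by learning the allocation comes at or after that hand-in, so in the planned sequence it cannot remove pain scores.

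Four further objections deserve weight.

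- **Safety capture.** Sections 7.4 and 9.2(b) require the study team to review and grade every complication, with no exception for withdrawn patients, and section 12.1 makes the primary surgeon a co-investigator. A complication seen at an open-date visit may well be captured. This stands, but it does not cover quality of life, symptom recurrence, or complications that do not bring the patient back.
- **Respect for withdrawal.** Some patients want no more contact, and ending calls is then right. This stands. The defect is that the same rule applies to patients who would have agreed.
- **Size.** The 10% is a rate of loss to follow-up, not of withdrawal, and continuing calls would not recover patients who cannot be reached. This stands. An extreme case can be built: assumed recurrence of 13/64 against 6/64 (10.9 points), with 6 leavers per arm, all recurrent in LAH and none in COH, would be seen as 7/58 against 6/58 (1.7 points). That combination is arithmetically possible, but nothing in the protocol makes it likely.
- **Unseen documents.** The consent form may already say what happens to data recorded before withdrawal. This is possible, so the fix is conditional on it. It would not undo the explicit cancellation of the calls.

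**Conclusion.** The point holds for the later secondary outcomes. Section 4.4.2 states a rule that removes the only scheduled 3-month and 1-year data for every voluntary withdrawal, including patients who would have agreed to give them. No later analysis can recover calls that were never made.

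The size is unknown. The 1 to 4 points rest on assumed withdrawal and recurrence rates and on the excess recurrence being confined to one arm's withdrawers; smaller or zero bias is equally compatible with the protocol. For the primary outcome there is a gap in the text and a small risk, not a stated loss. The stated sample size is not affected by this point.

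**What to change.** Amend section 4.4.2 as follows.

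1. Ask a withdrawing patient which parts of the trial they decline, and record the answer.
2. Keep the 3-month and 1-year calls unless the patient declines them.
3. Ask for the VAS package as completed so far, and keep data recorded to that date as consent allows.
4. Unless use of records is refused, take readmission, reoperation, complications and recurrence from hospital records to 1 year, including open-date visits. Mark these as record-based, because they are not equivalent to an interview.
5. Record the date and reason of each withdrawal, and report them by arm.
6. Align the consent form if it does not already provide for this.

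The cost is a short protocol and consent amendment plus a few extra calls and record look-ups. Even if the whole 10% allowance were withdrawals, that would be 0.10 × 128 = 12.8, or about 13 patients. No visit is added and clinical care is unchanged. The amendment is best made early, since interviews missed before then may not be recoverable.

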## **5 TRIAL MATERIALS**

### **5.1 Trial Product (s)**

NA

### **5.2 Storage and Drug Accountability**

NA

## **6 TREATMENT**

### **6.1 Rationale for Selection of Dose**

NA

## **6.2 Study Drug Formulations**

NA

## **6.3 Study Drug Administration**

NA.

## **6.4 Specific Restrictions / Requirements**

NA

## **6.5 Blinding**

Patients will be allocated only after they are examined under anaesthesia. Allocation is provided in a concealed opaque enveloped that is provided by the research administrator on the day of the operation. Thus, the patient is blinded to the procedure. There will also be no cross-over from one study arm to another.

An independent research administrator would conduct a phone interview with the patients at 3-month and 1-year after surgery to perform the QoL survey and also looking out for late-onset complications and recurrence of symptoms. If present, they will be offered to have an appointment booked with their primary surgeon. Patients would be informed of the allocation at the clinic review at 4-6 weeks.

## **6.6 Concomitant therapy**

NA

# **7 SAFETY MEASUREMENTS**

## **7.1 Definitions**

An adverse event (AE) is any untoward medical occurrence in a patient or clinical investigation subject administered a pharmaceutical product and which does not necessarily have a causal relationship with this treatment. An adverse event (AE) can therefore be any unfavourable and unintended sign (including an abnormal laboratory finding), symptom, or disease temporally associated with the use of a medicinal (investigational) product, whether or not related to the medicinal (investigational) product.

A serious adverse event (SAE) is any untoward medical occurrence that at any dose:

- results in death
- is life-threatening
- requires inpatient hospitalisation or prolongation of existing hospitalisation
- results in persistent or significant disability/incapacity, or
- is a congenital anomaly/birth defect

## **7.2 Collecting, Recording and Reporting of Serious Adverse Events (SAEs) to CIRB**

Only related SAEs (definitely/ probably/ possibly) will be reported to CIRB. Related means there is a reasonable possibility that the event may have been caused by participation in the clinical trial. Please refer to the CIRB website for more information on Reporting Requirement and Timeline for Serious Adverse Events.

The investigator is responsible for informing CIRB after first knowledge that the case qualifies for reporting. Follow-up information will be actively sought and submitted as it becomes available.

Related AEs will not be reported to CIRB. However, the investigator is responsible to keep record of such AEs cases at the Study Site File.

## **7.3 Collecting, Recording and Reporting of Serious Adverse Events (SAEs) to the Health Science Authority (HSA)**

All SAEs that are unexpected and related to the study drug will be reported to HSA. Please refer to the HSA website for more information on Safety Reporting Requirements for Clinical Trials.

## **7.4 Safety Monitoring Plan**

The Data Safety Monitoring Plan (DSMP) for this study can be divided into individual events and collated events.

Every individual complication will be evaluated by all members of the study team immediately after the event has occurred. The study team would review the case and its proceedings to determine whether the event was a direct result of the procedure or its technique, and whether this could have been prevented. The complication would also be scored for its severity based on the Clavien-Dindo Classification of Complications. If there is a severe complication, or if the complication is a direct result of the procedure or its technique, a technical pause would be called for in order to re-clarify the technical aspects as well as processes to avoid a repeat complication before the trial is resumed.

Interim analysis would also be carried out in a timely fashion (after 50% and 75% of the required sample size has been randomised). This would allow statistically significant differences in the outcome of the procedures to be identified. If one arm is grossly different from the other, the study team would convene to evaluate whether this outcome difference is regarded as a safety hazard to subsequent patients. If so, the trial would be halted or terminated prematurely.

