## **4 STUDY DESIGN**

This is a single-center, double-blind randomized controlled trial to be conducted in Sengkang General Hospital.

All patients presenting to the clinic or admitted for symptomatic haemorrhoids would be assessed for recruitment.

Figure 1 shows the enrolment process of the study population in the trial. Patients will be seen in the

clinic or in the wards for symptomatic haemorrhoids. All these patients would be approached and be introduced to this study but not recruited yet.

Patients older than 40 years-old with no recent colonoscopy (within 5 years) would need to have a colonoscopic evaluation of the colon after the index admission/clinic visit.

Those younger than 40 would be advised to have a rigid sigmoidoscopy on the day of the operation during the examination under anaesthesia. Only after agreement to the above, the patient would be recruited into the study. They would then be educated on the peri-operative questionnaire separately by a research administrator after recruitment into the trial.

The peri-operative package is split into pre- and post-operative components and will include basic demographics, baseline haemorrhoid-specific QoL questionnaires, VAS scales for POD0-10 and details of the intraoperative procedure and intraoperative description of the haemorrhoids.

Patients who fit the inclusion and exclusion criteria would be recruited into the study. We will perform a 1:1, block-of-4 randomization using a computer-generated programme performed by an independent research administrator who is not part of the surgical team.

They will be allocated only after they are examined under anaesthesia. Allocation is provided in a concealed opaque envelope that is provided by the research administrator on the day of the operation. Thus, the patient is blinded to the procedure. There will also be no cross-over from one study arm to another.

Potential Difficulties and Alternative Approaches to achieve the aims:

Difficulty of recruitment of patients into the trial may be potentially present especially for a procedure that is new in Singapore. Patient counselling and explanation of the procedure would be important and offering a short video clip of the procedure may be helpful. The procedurists/co-investigators of the study team would also be trained by a regional practitioner of the technique before the initiation of the trial to ensure proficiency for reassurance.

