## **8.2 Data Entry and Storage**

Data will be entered into a data collection sheet by the study team or on the peri-operative package by the patient. All these data will be scanned in and images stored in a dedicated encrypted external hard-drive for archiving purposes. Hard-copy forms will be stored in a ring-file that is kept under lock-and-key by the PI. The data on the 2 data collection forms will be separately entered into an password-protected excel document, not having any patient identifiers, and stored in the dedicated encrypted hard-drive in a separate folder for the purposes of data analysis.

Only the study administrators and study co-investigators will have access rights for data entry and analysis though the PI.

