## **9 SAMPLE SIZE AND STATISTICAL METHODS**

### **9.1 Determination of Sample Size**

Based on previous studies, as well as unpublished results from surgeons who have performed LAH around the South East Asian region, we are expecting 50% of the patients in the COH arm to have a VAS score of more than 7.5. We expect to see 25% patients in the LAH arm having a VAS score of more than 7.5.

With a power of 80%, chance of type 1 error (alpha) less than 5% and accounting for 10% of loss to follow up rate, the sample size required for the study to be adequate powered is having 64 patients in each arm (N=128).

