#### **b. Safety Analyses**

Every individual complication will be evaluated by all members of the study team immediately after the event has occurred. The study team would review the case and its proceedings to determine whether the event was a direct result of the procedure or its technique, and whether this could have been prevented. The complication would also be scored for its severity based on the Clavien-Dindo Classification of Complications. If there is a severe complication, or if the complication is a direct result of the procedure or its technique, a technical pause would be called for in order to re-clarify the technical aspects as well as processes to avoid a repeat complication before the trial is resumed.

c. Interim Analyses

Interim analysis would also be carried out in a timely fashion (after 50% and 75% of the required sample size has been randomised). This would allow statistically significant differences in the outcome of the procedures to be identified. If one arm is grossly different from the other, the study team would convene to evaluate whether this outcome difference is regarded as a safety hazard to subsequent patients. If so, the trial would be halted or terminated prematurely.

d. Describe the types of statistical interim analyses, including their timing.

Interim analysis would also be carried out in a timely fashion (after 50% and 75% of the required sample size has been randomised). This would allow statistically significant differences in the outcome of the procedures to be identified. If one arm is grossly different from the other, the study team would convene to evaluate whether this outcome difference is regarded as a safety hazard to subsequent patients. If so, the trial would be halted or terminated prematurely.

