## **12.1 Informed Consent**

Upon satisfaction of the inclusion and exclusion criteria, the primary surgeon (co-investigator) would introduce the trial to the patient in their preferred language either themselves or through a proxy. Upon interest, the research administrators will provide further details of the trial to the patient in a separate room in the clinic/wards. The patient will have ample time to read the patient information form (in the language that the patient can read) and consider enrolment into the trial. After the decision to participate, he/she would be invited to sign on the recruitment consent forms.

The research administrator and co-investigators would have to document the consult and the risks that of participation and of the techniques that were explained. In obtaining and documenting informed consent, the investigator should comply with the GCP guidelines and to the ethical principles that have their origin in the Declaration of Helsinki.

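### By-arm interim comparisons go to a study team whose co-investigators also recruit, operate and grade complications, with no step to keep the results from them

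*Protocol*

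**What the plan says.** Protocol 7.4 plans two interim analyses, and 9.2 c and 9.2 d repeat the text. Their purpose is comparative: "This would allow statistically significant differences in the outcome of the procedures to be identified". The reviewing body is named: "If one arm is grossly different from the other, the study team would convene to evaluate whether this outcome difference" amounts to a safety hazard, in which case the trial may be stopped. Section 4.4.1 c separately lists overwhelming statistical evidence of superiority as a ground for discontinuing.

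On access, 8.2 (repeated in 12.2 and 14) says: "Only the study administrators and study co-investigators will have access rights for data entry and analysis", through the PI. The biostatistician in 9.2 a helps with or validates the analyses, but is not on that access list.

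On roles:
- Section 4 equates surgeons and co-investigators: "The procedurists/co-investigators of the study team would also be trained".
- Section 12.1 has them open the consent discussion: "the primary surgeon (co-investigator) would introduce the trial to the patient".
- Section 3.2 has the PI or co-PIs evaluate candidates.
- Sections 7.4 and 9.2 b have every member of the study team evaluate each complication, judge whether the procedure caused it, and score its severity.

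Sections 4, 4.1 and 6.5 provide the protection: allocation by opaque envelope after examination under anaesthesia, patients told their arm only at the 4-6 week clinic review, and 3-month and 1-year calls made by an independent research administrator.

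**The concern.** Surgeons cannot be blinded to the operations they perform. They would not, however, otherwise see the accumulated patient-reported results by arm, because patients record VAS themselves in a package that research administrators collect. As written, the interim looks supply that information, or at least do nothing to withhold it, while recruitment and surgery continue.

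The hypothesis in 2.1 already favours LAH. A team that has seen one arm ahead may approach different patients, care for the two arms differently around and after surgery, or judge later complications differently. Bleeding and procedure-related complications are secondary outcomes under 2.3, so that judgement feeds the trial's results. If the looks exist to detect a safety hazard, that purpose does not require recruiting surgeons to see pain or QoL by arm.

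This arrangement is stated in the protocol. It is not a detail left for a SAP to fill in.

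**Working it through.** **Step 1: the denominator.** Section 9.1 gives the design inputs: "With a power of 80%, chance of type 1 error (alpha) less than 5% and accounting for 10% of loss to follow up rate", and "we are expecting 50% of the patients in the COH arm to have a VAS score of more than 7.5", against 25% in the LAH arm. Sidedness is not stated; I assume two-sided. With pooled variance, p̄ = (0.50 + 0.25)/2 = 0.375, and

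n = [1.960·√(2·0.375·0.625) + 0.842·√(0.50·0.50 + 0.25·0.75)]² / (0.50 − 0.25)²
= (1.342 + 0.557)² / 0.0625 ≈ 57.7, so 58 per arm.

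For 10% loss, 58 × 1.10 = 63.8, so 64, and 58/0.90 = 64.4, so 65. The planned 64 per arm (128) is reproduced, and N = 128 is used below.

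**Step 2: patients randomised after each look.** The number is N × (1 − f), where f is the fraction randomised.
- First look: 128 × 0.50 = 64 randomised; 128 − 64 = 64 remain (50%).
- Second look: 128 × 0.75 = 96 randomised; 128 − 96 = 32 remain (25%).

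**Step 3: why these are upper bounds.** The trigger is randomisation, which happens on the day of surgery, but the VAS package is collected at the 4-6 week visit (4.3.1). If recruitment continues at r patients per week, a complete first look leaves between 64 − 6r and 64 − 4r patients, and a complete second look between 32 − 6r and 32 − 4r (not below zero). The protocol gives no r and states no pause, so I put no number on the reduction.

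**Step 4: where knowledge of the comparison could act.**
- *Selection and introduction of the trial (3.2, 12.1).* These precede allocation. Research administrators then give the details separately. Knowledge can change who enrols and the overall level of expected pain, but it has no obvious arm-specific route.
- *Surgery and later care.* The surgeon knows the arm, so an arm-specific effect is possible.
- *VAS recording.* It is done by the patient over POD0-10, after instruction before surgery, and while blinded. It is largely protected.
- *Attribution and grading of complications (7.4, 9.2 b).* The whole team does this, including surgeons who know the arm, so an arm-specific effect is possible.
- *Clinic visit at 4-6 weeks (4.3.1).* The clinician is not identified as a co-investigator, and the visit falls after the VAS period.
- *Calls at 3 months and 1 year (4.1, 6.5).* These are made by an independent administrator. The protocol does not say whether that person is among the study administrators with analysis access in 8.2.

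**The case against.** The case on the other side is substantial. The team convenes only on a gross difference, and the question put to it is one of safety. The text does not say who prepares the tables or that they circulate at each look. Surgeons know each allocation and the team already reviews every complication, so it can tally complications by arm without an interim analysis. VAS is self-recorded by blinded patients.

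Most of this stands and narrows the point. Three stronger readings might be inferred, and the documents do not support them:
- *That the surgeons will learn which arm has less pain at both looks.* Pain is not named in 7.4, and convening is conditional. It is a reasonable inference, since pain is the primary outcome and 4.4.1 c allows stopping for superiority, but it is not stated.
- *That exactly half the trial would run with informed staff.* Step 3 shows that 64 and 32 are ceilings.
- *That the primary result would drift towards the leading arm.* Expectations set before allocation reach both arms alike, and a blinded patient cannot apply them by arm. No direction is shown.

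The objection does not remove the core. Someone must see the comparison before a gross difference can be recognised, and 8.2 gives access only to administrators and co-investigators. A decision not to convene is itself informative. What the looks add beyond the surgeons' own knowledge is mainly pooled VAS and QoL by arm, together with a formal comparison.

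**Conclusion.** The point holds in a limited form. The protocol gives review of between-arm interim comparisons to a team whose co-investigators operate, introduce the trial and judge complications, and it sets no barrier to circulation. At most 64 of 128 patients (50%) follow the first look and at most 32 (25%) the second. The risk lies in recruitment, in peri-operative and post-operative care by unblinded surgeons, and in attribution and grading of complications. Its size and direction cannot be derived from the protocol, and recording of the primary VAS is largely protected.

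This assumes that the looks include outcomes beyond complications, as the wording on procedure outcomes and 4.4.1 c suggest, and that recruitment continues through them. It is an avoidable weakness with a cheap remedy, and it does not threaten the trial's validity on its own.

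**What to change.** 1. In 7.4 and 9.2 c/d, have the biostatistician already in 9.2 a prepare the by-arm interim tables. Grant that person data access in 8.2, and align the same access wording in 12.2 and 14.
2. Report to the study team only whether a between-arm safety difference, or the superiority ground in 4.4.1 c, has been flagged. Release the by-arm data needed for the decision only if one has. Without the second flag, nobody could act on 4.4.1 c.
3. Otherwise, withhold VAS by arm from anyone who recruits, operates or assesses until the last POD0-10 package is in. Withhold QoL, complication and recurrence summaries by arm from the same people and from the telephone interviewers until the last 1-year call, because those outcomes are still being collected until then. Limit the co-investigators' analysis access in 8.2 to match.
4. Leave the immediate review of individual complications unchanged.

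The cost is a wording amendment and some biostatistician time at two looks, with no extra patients and N still 128. The study team loses sight of running comparative results. It will still be able to count complications by arm from its own case reviews, so this reduces the exposure without eliminating it.
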